9.2.1 Sensitivity Analysis of Secondary Endpoints

- Exclusion of out of window visits: An analysis will be conducted excluding any out of window visits occurring more than +/- 30 days outside of the planned timepoints. Time-adjusted analysis: Time-adjusted analysis will be performed by adjusting the actual efficacy assessment results to the nominal timepoint, as described in Section 7.5.

9.3 Exploratory Efficacy Analyses

Any post hoc, exploratory analyses completed to support planned study analyses, which were not identified in this SAP, will be documented and reported in appendices in the CSR. Any results from these unplanned analyses will also be clearly identified as such in the text of the CSR.

10 SAFETY EVALUATION

All safety analyses will be performed for the Safety population. Each analysis will consist of a summary of data within each treatment group and overall.

Safety analyses will be performed on all participants who underwent either implant surgery or the sham procedure. The assessment of safety will be based on the summary of ocular and non-ocular treatment-emergent AEs (TEAEs) and ophthalmic examinations.

Safety analysis will include the Month 24 safety analysis, i.e. the set of data associated with the period from surgery through the Month 24 Visit.

The overall safety profile of the NT-501 implant versus sham will be assessed in terms of the following safety and tolerability endpoints:

- Incidence of treatment-emergent adverse events (TEAEs)
- Visual acuity
- Intraocular Pressure (IOP)
- Pupil Size

10.1 Treatment-Emergent Adverse Events (TEAEs)

The collection period of adverse events, serious and non-serious, will begin after surgery and continue throughout the course of the participant's participation in the study. For analysis purposes, all adverse events will be classified as TEAE.

The TEAEs will be presented by treatment group (NT-501 implant versus sham). Summaries for TEAEs include the following: all TEAEs regardless of causality, treatment-related TEAEs, ocular TEAEs, treatment-related ocular TEAEs, TEAEs by intensity, serious adverse events (SAEs), and TEAEs leading to discontinuation from the study.

All TEAEs will be coded using the Medical Dictionary for Regulatory Activities (MedDRA).

The incidence of TEAEs will be summarized for each treatment group by system organ class and preferred term. If a subject reports the same AE more than once, then that subject will only be counted once in the summary of that AE, using the most severe intensity.

AEs will be summarized through Month 24 and through the end of the trial/Month 48:

- All ocular TEAEs;
- All non-ocular TEAEs;
- All ocular TEAEs by intensity;
- All non-ocular TEAEs by intensity;
- All ocular TEAEs by relationship to surgical procedure/device/CNTF;
- All non-ocular TEAEs by relationship to surgical procedure/device/CNTF;
- Ocular SAEs;
- Non-ocular SAEs;
- Ocular SAEs by relationship to surgical procedure/device/CNTF;
- Non-ocular SAEs by relationship to surgical procedure/device/CNTF;
- Deaths; and
- Ocular/Non-ocular TEAEs that led to explantation of IP.

All SAEs and TEAEs leading to premature withdrawal from the study will be listed.

Summaries will be presented using frequency counts and percentages (i.e., the number and percentage of study eyes/participants with an event as well as the total number of events). Study eyes/participants with multiple occurrences of the same AE or a continuing AE will be counted once, and only the maximum severity level will be presented in the severity summaries, and the worst/highest relationship level in the relationship summaries. A separate table will summarize all TEAEs when each of them is considered unique, hereafter referred as AE count table. In addition, a listing containing individual participant adverse event data for all deaths and serious adverse events will be provided, separately. All adverse events will be presented in individual subject data listings.

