#### 3.2.2 Secondary Safety Endpoints

- Number and proportion of participants with a loss in BCVA of 15 or more letters from baseline in the study eye using the Early Treatment Diabetic Retinopathy Study (ETDRS) distance chart
- Number and proportion of participants with at least 1 treatment-emergent serious adverse event (SAE)

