## 4. STUDY PLAN

### 4.1 STUDY DESIGN

This is a Phase 3, prospective, multicenter, masked, sham-controlled study of approximately 112 study participants with MacTel.

All participants are to be followed through the 24-Month Visit, where 1 month is defined as 30 days. Originally the subset of participants enrolled early into the study were to be followed through a 36-Month Visit and/or a 48-Month Visit, based on the date of the surgical procedure. The rate of change in the EZ (IS/OS) area loss over the Month-36 and Month 48 time points were identified as secondary endpoints. A decision has been made to discontinue the Month-36 and Month 48 study visits because the limited number of subjects completing these

visits does not provide sufficient statistical power to demonstrate a treatment effect for these secondary endpoints. The Sponsor decision to terminate this study early is not related to any safety or any adverse event related to the study treatment or surgical procedures related to the implantation.

With the current protocol amendment, the changes to the study visit schedule include the following:

- (1) Subjects who will complete the Month-24 visit after 01 December 2021 will not complete their scheduled Month-36 and/or their Month-48 study visits. These study participants will exit the study when they complete the Month-24 visit.
- (2) Subjects who have completed the Month-24 visit and have Month 36 and/or Month 48 visits scheduled before or on 01 December 2021 will exit from the study after completing these scheduled visits.
- (3) Subjects who have completed the Month-24 visit and have Month 36 and/or Month 48 visits scheduled after 01 December 2021 will not complete these visits but will complete a safety check-in call and exit the study by 01 December 2021.

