### 10.1 DOCUMENTING ADVERSE EVENTS

All AEs, either observed by the investigator or their medical collaborators, or reported by the participant spontaneously, or in response to direct questioning, will be reported. Any AE regardless of severity or potential association with the NT-501 device, CNTF, or the study procedures must be documented in study records by the investigator and appropriately reported.

All AEs will be reported within the participant's records and in the EDC system. All AEs should be entered into the data system as soon as possible after identification by the site personnel. All AEs will be recorded from the time of surgery until the last study visit.

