1 PREFACE

This statistical analysis plan (SAP) is for the data collected through the Month 24 time point in the clinical study protocol titled “A Phase III randomized, sham controlled, study to determine the safety and efficacy of NT-501 in macular telangiectasia type 2” (NTMT03-A). This SAP describes and expands upon the statistical information presented in the protocol.

This document describes all planned analyses and provides reasons and justifications for these analyses. It also includes sample tables, figures, and listings planned for the final analyses in the Clinical Study Report (CSR).

This SAP follows the International Conference on Harmonisation of Technical Requirements for Registration of Pharmaceuticals for Human Use (ICH) Guidelines, as indicated in Topic E3 (Structure and Content of Clinical Study Reports), and more generally is consistent with Topic E8 (General Considerations for Clinical Trials) and Topic E9 (Statistical Principles for Clinical Trials). The structure and content of the SAP provides sufficient detail to meet the requirements identified by the US Food and Drug Administration and ICH, while all work planned and reported for this SAP will follow internationally accepted guidelines published by the American Statistical Association and the Royal Statistical Society for statistical practice.

This document contains a review of the study design, general statistical considerations, comprehensive statistical analysis methods for efficacy and safety endpoints, and a list of proposed tables, figures, and listings. If revisions to this SAP are needed, the document will be amended. All SAP amendments will be finalized prior to the database lock. All deviations from the analyses described in the final SAP will be noted in the CSR.

Neurotech Pharmaceuticals, Inc or a designated Contract Research Organization (CRO) will perform the statistical analysis of the efficacy and safety data; SAS version 9.1.3 or higher will be used to generate all statistical outputs (tables, figures, listings and datasets). The SAP will be finalized and approved prior to the final clinical data lock for the study.

The reader of this SAP is encouraged to also review the study protocol for details on conduct of the study and the operational aspects of clinical assessments.

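### The AE tables running to the end of trial/Month 48 use crude percentages over everyone operated on, although follow-up after Month 24 is cut by calendar date; any event type that still occurs after Month 24 would be understated.

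*SAP*

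**What the plan says.** SAP 10.1 sets two horizons: "AEs will be summarized through Month 24 and through the end of the trial/Month 48". The measure is also stated: "Summaries will be presented using frequency counts and percentages", meaning "the number and percentage of study eyes/participants with an event as well as the total number of events". For the denominator, SAP 10 says "All safety analyses will be performed for the Safety population". SAP 7.3.3 defines that set as everyone randomised and operated on, implant or sham, who has any safety measurement. It does not shrink after Month 24.

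Observation time does shrink. Protocol 10.1 says "All AEs will be recorded from the time of surgery until the last study visit". Under Protocol 4.1 (version 7.0), participants whose Month 24 visit falls after 01 December 2021 leave at that visit. Those past Month 24 with a later visit due by that date leave after it. Those past Month 24 with a later visit due after that date "will not complete these visits but will complete a safety check-in call and exit the study by 01 December 2021". SAP 4.1 instead has one common end date, about August 2022, and accepts that not everyone will reach Months 36 and 48.

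Elsewhere the SAP stops at Month 24. Its Preface says it is "for the data collected through the Month 24 time point", SAP 10 names only the period from surgery to Month 24, and Appendix C shows 24 in every safety row. Kaplan-Meier appears once, in SAP 8.1, for premature discontinuation.

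**The concern.** The two AE tables will sit side by side and share a denominator. A reader will naturally take one as risk by 24 months and the other as risk by 48. The second numerator, however, can only collect events from people still observed after Month 24, while the denominator keeps those who left at Month 24.

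A small rise from the first table to the second then has two explanations: few new events occurred, or few people were there to have them. Crude percentages cannot tell these apart. NT-501 is meant to stay in the eye for the whole study, so whether events keep accumulating is a fair question to ask of any table that extends to Month 48.

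**Working it through.** The documents give no AE percentage, exposure total or post-Month-24 number at risk, so there is no planned figure to reproduce. What can be checked is how the measure behaves under stated assumptions.

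**Who can be followed how long.** With 30-day months, counting back from 01 December 2021:
- 48 months (1,440 days) needs surgery by 22 December 2017.
- 36 months (1,080 days) needs surgery by 17 December 2018.
- 24 months (720 days) needs surgery by 12 December 2019. Anyone operated on later has no follow-up after Month 24.

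If the last Month 24 visit is at the end of August 2022 (SAP 4.1), the last surgery is about 10 September 2020. The start of accrual is not given. I assume uniform accrual over 24 to 40 months.

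| | Protocol 4.1 rules | SAP 4.1 end date |
|---|---|---|
| No follow-up after Month 24 | 23% to 38% | about 0% |
| At least 36 months | 12% to 47% | 50% to 70% |
| Full 48 months | 0% to 17% | 0% to 40% |
| Mean follow-up in months 24 to 48 | 4.6 to 11.3 of 24 | 12.0 to 16.8 of 24 |

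The protocol column ignores exits at a completed Month 36 visit, which would shorten follow-up further. The SAP column assumes everyone stays to the end date.

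**Crude against true, constant hazard.** Let F(t) = 1 - exp(-λt), with F(24) = 0.20 assumed. Then 24λ = -ln 0.8 = 0.2231, and the true 48-month risk is 1 - 0.8² = 36.0%. The crude figure is the average of F over participants' exit times. For exits spread evenly over months 24 to 48 that average is 1 - (0.80 - 0.64)/0.2231 = 28.3%.
- Protocol rules, 40-month accrual: 17.25% reach 48 months, 60% are spread over 24 to 48, and 22.75% stop at 24. Crude = 0.1725 × 36.0 + 0.60 × 28.3 + 0.2275 × 20.0 = 27.7%.
- Protocol rules, 24-month accrual: 37.9% stop at 24 and the rest are spread over 24 to 38.9 months, with average F of 25.3%. Crude = 0.379 × 20.0 + 0.621 × 25.3 = 23.3%.
- SAP end date, 24-month accrual: all are spread over 24 to 48, so 28.3%. With 40-month accrual: 0.40 × 36.0 + 0.60 × 28.3 = 31.4%.

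**Dependence on the late hazard.** Here I use assumed shares exiting at 24/36/48 months, again with 20% affected by Month 24.

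| Hazard after Month 24 | True 48-month risk | Crude, 80/15/5 | Crude, 60/30/10 | Crude, 40/40/20 |
|---|---|---|---|---|
| Same as before | 36.0% | 22.1% | 24.1% | 26.6% |
| Half | 28.4% | 21.1% | 22.1% | 23.4% |
| None | 20.0% | 20.0% | 20.0% | 20.0% |

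In the first row the table shows (22.1 - 20)/16 = 13%, 26% or 41% of the true increase.

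**Between arms.** Take 60/30/10 in both arms, a constant hazard, and Month 24 risks of 20% and 10%. The crude figures are 24.1% and 12.3%: difference 11.8 points, ratio 1.96. With full follow-up they are 36.0% and 19.0%: difference 17.0 points, ratio 1.89.

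**Person-time.** In the 60/30/10 case, first events divided by time at risk give 11.2 per 100 participant-years, which is the assumed rate (0.2231/24 × 1,200).

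**The case against.** The strongest reply is that the documents point to mainly early events. Protocol 1.2.4 says most AEs came from the implantation procedure and that the majority settle within days. Protocol 1.1 says postoperative inflammation typically clears by 3 months, and its one delayed Phase 2 case was noted at 6 months. For such events a flat second table would be true. This stands, and it makes the concern conditional. It does not remove it: the SAP 10.1 list also covers deaths, non-ocular events, SAEs and explantation, for which a zero rate after Month 24 cannot simply be assumed.

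The SAP also never calls the longer figure a 48-month risk, says itself that not everyone reaches those visits, treats safety results as descriptive, and lists every AE individually. That is fair, and it limits the harm. Still, a reader given one percentage and no exposure cannot make the correction.

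Three stronger readings are tempting and are not supported:
- *The longer table will certainly understate risk and show a false plateau.* That requires events after Month 24, and no passage gives a late event rate.
- *The comparison between arms is biased.* Allocation is 1:1 and the cut-off is a date, so both arms should lose follow-up alike. The ratio barely moves in the example, although the absolute difference shrinks.
- *The SAE endpoint mixes 24 to 48 months of exposure.* Protocol 3.2.2 sets no time limit, but SAP 3.2.2.2 limits the endpoint to Month 24. That is a wording mismatch, not a flaw in the planned endpoint.

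**Conclusion.** The point holds in conditional form. As a long-term risk, the planned percentage is too low for any event type that still occurs after Month 24, and correct for one that does not. How far too low cannot be derived, because the accrual dates, the exposure after Month 24 and the late event rate are all missing. The 23% to 28% (protocol rules) and 28% to 31% (SAP end date) against 36% rest on 20% affected by Month 24, a constant hazard and uniform accrual over 24 to 40 months. A falling hazard narrows the gap, to nothing in the limit.

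The Month 24 AE tables and the SAE endpoint as the SAP defines it are unaffected. Whatever the bias, two inconsistencies need resolving: SAP 10.1 goes beyond the Month 24 scope set elsewhere in the SAP, and the SAP's end date disagrees with the protocol's exit rules. This is a worthwhile, inexpensive improvement and not a threat to the trial's main conclusions.

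**What to change.** 1. Reconcile SAP 10.1 with the Month 24 scope in SAP 1, SAP 10 and Appendix C, and reconcile the end date in SAP 4.1 with the exit rules in Protocol 4.1.
2. Then choose one of two courses:
   - Drop the AE summaries to Month 48.
   - Keep them, and show by arm the participant-years, the first-event and total-event rates per 100 participant-years for months 0 to 24 and separately for after Month 24, and the numbers at risk at Months 24, 36 and 48. The split matters because one pooled rate would blend early surgical events with late ones. Treat sponsor-directed exits as administrative censoring. Quote Kaplan-Meier risks only up to times with enough participants at risk; under the shorter accrual assumption nobody reaches 48 months by the protocol's cut-off.
3. Align the SAE endpoint in Protocol 3.2.2 with the Month 24 limit in SAP 3.2.2.2.

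Dropping the tables needs only wording changes. Keeping them needs a few extra columns from surgery, event and exit dates already collected. The cost is wide intervals after Month 24, which is an honest picture of how little follow-up there is. The rates will also rest on yearly visits, against every four months between Months 12 and 24, and exposure adjustment does not cure that.

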10.2 Visual Acuity

Participants with 15 or more letters of vision loss from baseline in the study eye will be tabulated and presented by treatment group. A 2-sample test of proportions will be performed to determine if there is a significant difference in proportions between the treatment groups through Month 24.

10.3 Implant/Sham Site Examination

The number and percentage of study eyes with shifts deemed clinically significant in the implant surgical examination findings for the listed characteristics on the CRF from baseline to post-baseline will be tabulated by treatment group at each scheduled visit.

10.4 Surgical Medications

Surgical medications will be listed.

10.5 Ophthalmic Examination

Ophthalmic examination findings with attention to the presence or absence of retinal findings or grading of disease eye will be listed for the study eye for individual participants. Intraocular pressure (IOP), and pupil size, change in intraocular pressure and change from baseline pupil size at each study visit will be summarized using mean, SD, median, minimum and maximum by treatment group. Number and percent of participants with an IOP of 21 mm Hg or greater and an increase of 5 mm Hg or more from Baseline at post-operative visits will be summarized.

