## 10. ADVERSE EVENTS

An AE is any untoward medical occurrence in humans, whether or not considered treatment- or procedure-related, which occurs during the conduct of a clinical trial. Any change in clinical status, ophthalmological assessments, etc., that is considered clinically significant by the study investigator and requires intervention is considered an AE. Medical conditions or diseases present before a participant starts study treatment are only considered AEs if they worsen after the participant starts study treatment (temporal association).

A suspected adverse reaction (related AE) is any event for which there is a reasonable possibility that the treatment caused the AE. A reasonable possibility implies that there is evidence that the treatment caused the event.

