### 10.2 ASSESSMENT OF INTENSITY

#### Guidelines for Assessing Intensity of an Adverse Event

The investigator should use the following definitions when assessing intensity of an AE:

- **MILD:** Transient (< 48 hours) or mild discomforts, no or minimal medical therapy or intervention required, hospitalization not necessary, no or little limitation in normal activities
- **MODERATE:** Mild to moderate limitation in activity, some assistance may be needed; possibly none but usually minimal intervention/therapy required; hospitalization possible
- **SEVERE:** Marked limitation in activity, some assistance usually required; medical intervention/therapy required; hospitalization possible or likely

- **LIFE-THREATENING:** Extreme limitation in activity, significant and immediate assistance required; significant medical/therapy intervention required to prevent loss of life; hospitalization, emergency treatment, or hospice care probable
- **FATAL:** Death

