### 12.3.3 Analysis of Safety

Safety analyses will be performed on all participants who underwent either implant surgery or the sham procedure. The assessment of safety will be based on the summary of ocular and nonocular treatment-emergent AEs (TEAEs) and ophthalmic examinations. The Medical Dictionary for Regulatory Activities (MedDRA) nomenclature will be used to code AEs.

The TEAEs will be presented by treatment group (NT-501 versus sham). Summaries for TEAEs include the following: all TEAEs regardless of causality, treatment-related TEAEs, ocular TEAEs, treatment-related ocular TEAEs, TEAEs by intensity, SAEs, and TEAEs leading to discontinuation from the study.

The number and proportion of participants with a loss in BCVA of 15 or more letters from baseline in the study eye will be tabulated and presented by treatment group.

Detailed methods for the analysis of all endpoints will be outlined in the SAP.

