4.4.2 Safety Variables

Safety will be evaluated by monitoring AEs and SAEs, results of ophthalmic examinations (including slit-lamp biomicroscopy and dilated fundus parameters, as well as measurements of BCVA and intraocular pressure [IOP]).

All AEs will be captured whether or not considered to be related to the surgical procedure, implant, or CNTF. The incidence of reported AEs will be compared between the treated and sham participants, particularly with respect to ocular AEs. An attempt will be made to differentiate between treatment-

related AEs and AEs considered to be part of the normal progression of the disease. In addition, for treatment-related AEs, an attempt will be made to differentiate those that the investigator believes are due to the device itself, to CNTF, or to the implant/sham procedure.

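### Slit-lamp and dilated-fundus findings are planned as participant listings only, which leaves a narrow set of lens, corneal and anterior-chamber changes with no by-arm summary (minor, cheap to improve)

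*SAP*

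**What the plan says.** SAP 4.4.2 states that safety will be evaluated by monitoring, among other things, "results of ophthalmic examinations (including slit-lamp biomicroscopy and dilated fundus parameters", alongside BCVA and IOP. Protocol 12.3.3 says "The assessment of safety will be based on the summary of ocular and nonocular treatment-emergent AEs (TEAEs) and ophthalmic examinations", and SAP 10 repeats this almost word for word. SAP 10 also states, for all safety analyses, "Each analysis will consist of a summary of data within each treatment group and overall".

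SAP 10.5 is the section that specifies output for the examinations. It says "Ophthalmic examination findings with attention to the presence or absence of retinal findings or grading of disease eye will be listed for the study eye", by individual participant. By treatment group it summarises only IOP and pupil size, their changes, and the count of participants meeting an IOP criterion. Appendix C agrees: its Ophthalmic Examination block has two rows, change in IOP and change in pupil size.

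Three other sections give by-arm output that overlaps with these examinations. On adverse events, SAP 10.1 says "The incidence of TEAEs will be summarized for each treatment group by system organ class and preferred term". SAP 10.3 tabulates clinically significant shifts in the site-examination characteristics on the CRF, by arm and visit. SAP 10.2 compares the proportion losing 15 or more letters.

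**The concern.** The general text leads a reader to expect a by-arm summary of examination findings, while the section that specifies the output directs a listing. The two arms differ physically: one receives an intraocular implant, the other a superficial conjunctival procedure. Cataract is among the surgical risks named in Protocol 13. Exclusion criterion 11 bars lens opacities only above set AREDS standards, so a participant can enter with some opacity that later progresses.

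If a slit-lamp or fundus change falls outside the other tables, the only way to compare arms is to read individual listings. What is at stake is the completeness of the descriptive safety comparison.

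**Working it through.** The plan states no figure on this point, so the check is mainly a comparison of texts.

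1. **Is there a by-arm table for slit-lamp or fundus findings as such?** No. SAP 10.5 lists them, Appendix C has no row for them under Ophthalmic Examination, and the wording in SAP 10 names no such table.

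2. **What reaches a by-arm table through adverse events?** A good deal. Protocol 10 opens broadly: "An AE is any untoward medical occurrence in humans". Protocol 10.1 adds: "Any AE regardless of severity or potential association with the NT-501 device, CNTF, or the study procedures must be documented in study records". The MILD grade in Protocol 10.2 allows for "no or minimal medical therapy or intervention required". A change reported as even a mild event is therefore tabulated by arm under SAP 10.1. What this route misses is change that the investigator does not report. Reporting may vary, because the sentence in Protocol 10 that deals specifically with ophthalmological assessments speaks of changes that are clinically significant and need intervention. Untreated, slowly progressing lens change is the obvious candidate.

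3. **What reaches a by-arm table through the site examination?** Appendix C has 15 shift rows. They include vitreous inflammation, intraocular hemorrhage, tractional retinal detachment, CNV and sectorial lens opacification. One of the 15 concerns the lens; none names the cornea or anterior-chamber inflammation. SAP 10.3 limits the table to shifts deemed clinically significant and to characteristics on the CRF, whose list may be longer than Appendix C.

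4. **What reaches a by-arm table through acuity?** Only change severe enough to cost 15 or more letters (SAP 10.2).

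5. **What remains?** Mainly lens change other than sectorial opacification, and corneal or anterior-chamber change, that is not reported as an adverse event and is not on the CRF site-examination list.

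6. **Could the table be built from planned data?** The schedule of events has both examinations at screening and, through Month 24, at Day 1, Week 1 and Months 6, 12, 16, 20 and 24 (also Months 1 and 3 in France). Baseline and follow-up examinations therefore exist. Whether each finding is a CRF field at both times cannot be seen from the documents.

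7. **What could such a table show?** The documents give no rates for these findings, so a range is assumed. With n = 56 per arm (Protocol 12.2, SAP 5) and the same proportion p in both arms, the half-width of the 95% interval for the difference is 1.96 × √(2p(1 − p)/56):
   - p = 0.10: 1.96 × √(0.18/56) = 11.1 percentage points
   - p = 0.20: 1.96 × √(0.32/56) = 14.8 points
   - p = 0.30: 1.96 × √(0.42/56) = 17.0 points

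**The case against.** The best defence is that this is a reporting preference. SAP 10 goes on to name the safety and tolerability endpoints: TEAEs, visual acuity, IOP and pupil size. All four are summarised by arm. Slit-lamp and fundus findings are not among them, nor among the secondary safety endpoints in SAP 3.2.2.2. SAP 4.4.2 speaks only of monitoring, and the general phrase about summarising ophthalmic examinations can be met by the IOP and pupil-size tables. Listing ungraded observations from an unmasked ophthalmologist (Protocol 5.6), made by site-standard procedures (Protocol 7.1), is defensible.

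Much of this stands. It rules out three stronger readings that a reader might infer:

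- *That the SAP breaks a commitment to tabulate these findings.* The general wording is too loose for that, and the named endpoint list points the other way.
- *That slit-lamp and fundus findings have no by-arm cover, so cataract or intraocular inflammation would go unseen.* Cataract reported as an adverse event is tabulated by preferred term, and vitreous inflammation has its own shift row.
- *That an examination change counts as an adverse event only if it needs intervention.* Protocol 10 does not say only; that sentence follows the broad definition and does not narrow it.

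The objection also shows that a table of worsening would need a definition. AREDS lens grading appears only as an eligibility criterion, and the documents define no scale for later visits. The fix below therefore uses shifts that the CRF can support.

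The objection does not remove the residue in step 5. For that residue the plan offers only a listing, and the adverse-event and site-examination routes both depend on a judgement about reporting or clinical significance.

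**Conclusion.** The point holds in this limited form: a minor gap in descriptive safety reporting, and a cheap improvement rather than an error. It concerns only lens, corneal and anterior-chamber change that escapes the adverse-event tables, the site-examination shifts and the acuity comparison. The primary analysis, power, type I error and every named safety endpoint are unaffected.

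Its size cannot be measured from the documents, because they give neither the rates of such findings nor the CRF. If the CRF site-examination list already covers lens and anterior-segment findings, the gap shrinks to shifts not deemed clinically significant. On the assumed rates, the extra table would resolve differences of roughly 11 to 17 points at best, so it guards against a large imbalance and cannot establish that a small one is absent.

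**What to change.** Check the CRF fields first. Then keep the listing in SAP 10.5 and add text such as:

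*For each slit-lamp and dilated-fundus finding held as a CRF field both at baseline and after baseline, the number and percentage of study eyes with a shift from baseline (absent to present, normal to abnormal, or a higher grade where the CRF records one) will be tabulated by treatment group, at any visit through Month 24 and at Month 24. The table is descriptive, without p-values. Findings without such fields remain in the listing.*

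Add a matching row under Ophthalmic Examination in Appendix C, and a footnote to the table that the examining ophthalmologist is unmasked and that examinations follow each site's standard procedures.

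The cost is one SAP paragraph, one appendix row and one table, with no new visits or assessments. There are two drawbacks. Small differences between arms may reflect unmasked, unstandardised examination, which the footnote says. The any-visit column will also pick up expected early postoperative change in the implant arm, which is why the Month 24 column is needed beside it.
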